11.0 Data Quality Assurance

Prior to the initiation of the study, a meeting will be held with AbbVie personnel, the Investigators and appropriate site personnel. This meeting will include a detailed discussion of the protocol, performance of study procedures, eCRF, Subject Questionnaires and Subject Dosing Sheet completion, and specimen collection methods.

The AbbVie CRA will monitor each site throughout the study, and source document verification will be performed.

All data entered in the database will be verified at AbbVie. Any discrepancies will be reviewed. The data will be reviewed and computer logic checks will be run to identify items such as inconsistent study dates. A manual review of selected line listings also will be performed at the end of the study. Queries will be generated in the EDC system. Any necessary corrections will be made to the eCRF.

The data from the central laboratory analyses will be electronically transferred from the central laboratory to the study database. A final review of all laboratory results will be conducted by a physician and clinical review team at AbbVie.

13.0 Completion of the Study

The investigator will conduct the study in compliance with the protocol and complete the study within the timeframe specified in the contract between the Director of the Site and the sponsor. Continuation of this study beyond this date must be mutually agreed upon in writing by both the Director of the Site and the sponsor. The investigator will provide a final report to the Director of the Site following conclusion of the study, and the Director of the Site will inform the summary of the report to IRB and the sponsor.

The Director of the Site must retain any records related to the study according to local requirements. If the Director of the Site is not able to retain the records, he/she must notify the sponsor to arrange alternative archiving options.

AbbVie will select the signatory investigator from the investigators who participate in the study. Selection criteria for this investigator will include level of participation as well as significant knowledge of the clinical research, investigational drug and study protocol. The signatory investigator for the study will review and sign the final study report in accordance with the European Medicines Agency (EMA) Guidance on Investigator's Signature for Study Reports.

The end-of-study is defined as the date of the last subject's last visit or the actual date of follow-up contact, whichever is later.

Appendix A. Responsibilities of the Clinical Investigator

Clinical research studies sponsored by AbbVie are subject to the Good Clinical Practices (GCP) and local regulations and guidelines governing the study at the site location. In signing the Investigator Agreement in Section [14.0](#) of this protocol, the investigator is agreeing to the following:

1. Conducting the study in accordance with the relevant, current protocol, making changes in a protocol only after notifying AbbVie, except when necessary to protect the safety, rights or welfare of subjects.
2. Personally conducting or supervising the described investigation(s).
3. Informing all subjects, or persons used as controls, that the drugs are being used for investigational purposes and complying with the requirements relating to informed consent and ethics committees (e.g., independent ethics committee [IEC] or institutional review board [IRB]) review and approval of the protocol and amendments.
4. Reporting adverse experiences that occur in the course of the investigation(s) to AbbVie and the site director.
5. Reading the information in the Investigator's Brochure/safety material provided, including the instructions for use and the potential risks and side effects of the investigational product(s).
6. Informing all associates, colleagues, and employees assisting in the conduct of the study about their obligations in meeting the above commitments.
7. Maintaining adequate and accurate records of the conduct of the study, making those records available for inspection by representatives of AbbVie and/or the appropriate regulatory agency, and retaining all study-related documents until notification from AbbVie.
8. Maintaining records demonstrating that an ethics committee reviewed and approved the initial clinical investigation and all amendments.

9. Reporting promptly, all changes in the research activity and all unanticipated problems involving risks to human subjects or others, to the appropriate individuals (e.g., coordinating investigator, institution director) and/or directly to the ethics committees and AbbVie.
10. Following the protocol and not make any changes in the research without ethics committee approval, except where necessary to eliminate apparent immediate hazards to human subjects.

Appendix C. Clinical Expense and Compensation

Expenditure of the Clinical Expense

The sponsor will pay the expenses related to this study to the investigative site in accordance with "Special Healthcare Expenditure." The expenses of screening test, etc. will be paid based on the contract concluded with each investigative site. To lighten the burden imposed on the subject with participation to the study, transportation expenses, etc. will be paid to the subjects via participating investigative site in accordance with the rules of the investigative site.

Compensation for Health Impairment and Insurance

1. If a subject suffers some sort of health impairment due to this study, the investigative site will provide treatment and take other necessary measures. Among the expenses required for the treatment, the amount not covered by health insurance that the patient must pay directly will be borne by the sponsor only when the event is associated with the use of the study drug.
2. When a subject suffers health impairment during this study and a dispute occurs or might occur between the investigative site and the subject, the investigative site will immediately report this to the sponsor and resolve it. The sponsor will cooperate with the investigative site in resolving any issues or problems.
3. When the investigative site must compensate subject for any health impairment caused by this study, the compensation paid by the investigative site and the expenses related to any dispute will be borne in full by the sponsor, except in cases where the responsibility for the problem is attributed to the investigative site. This shall not apply to cases where the health impairment occurred because the investigative site performed the study with marked deviation from the GCP or the protocol or because of a deliberate action or a major error by the investigative site.
4. When a subject suffers health impairment during this study and liability for compensation arises, the sponsor will compensate in accordance with the SOP regarding the compensation prepared in advance.

5. The sponsor will obtain clinical study insurance and will take other necessary measures to cover the claims and compensation required in such cases.

Appendix D. Screening Log – Sample

Name of the Investigation Site

#	Subject ID Number	Subject's Name		Sex	Age	Date of Informed Consent	Sending info to the Sponsor's CRA	First Administration	Date of the First Administration	Comments
		Last	First							
1				M / F	20	mon day			20	mon day
2				M / F	20	mon day			20	mon day
3				M / F	20	mon day			20	mon day
4				M / F	20	mon day			20	mon day
5				M / F	20	mon day			20	mon day
6				M / F	20	mon day			20	mon day
7				M / F	20	mon day			20	mon day
8				M / F	20	mon day			20	mon day

20 mon day Principal Investigator's Signature _____

Appendix E. Eligibility Assessment Form for Enrollment

FAX Number	Reporter	
AbbVie GK [name]	Study Institution	
	Department	Dermatology
	Investigator's name	

Subject ID Number		Date of Informed Consent	Date of Eligibility Assessment
		20  mon day 	20  mon day 
Sex	Age	Total Skin score	Score of Erythema with Pustule
M / F			

Inclusion Criteria

Yes	No	Not Applicable	
			1 Subject must be able and willing to provide written informed consent and comply with the requirements of this study protocol. If the subject is < 20 years old, a subject's parent or legal guardian must be willing to give written informed consent.
			2 Male or female ≥ 15 and ≤ 75 years of age at the Baseline visit.
			3 Subject must have a diagnosis of Generalized Pustular Psoriasis (GPP) for at least 60 days prior to Screening and determined by the Investigator through subject interview and review of medical history during the Screening Period.
			4 Subject must have had an inadequate response to, or demonstrated intolerance to, or have a contraindication to the currently approved treatment for their GPP (excluding infliximab).
			5 Subject must have total skin score of at least 3 and erythema with pustules (skin score of at least 1) in JDA severity index of GPP in GPP Medical Care Guideline 2014 in Japan at Baseline.
			6 Subject may be included if they have previously experienced a benefit for their GPP from infliximab and discontinued its use due to a subsequent loss of response or intolerance. Confirmed documentation indicating loss of response or lack of tolerability will be required.

Yes	No	Not Applicable	
			7 If female, subject is either not of childbearing potential, defined as postmenopausal for at least 1 year or surgically sterile (bilateral tubal ligation, bilateral oophorectomy and/or hysterectomy) or is of childbearing potential who must have negative result of pregnancy test performed at the Screening and at the Baseline. Female subject of childbearing potential is practicing an approved method of birth control throughout the study and for 150 days after last dose of study drug.
			8 If female, subject is not breast-feeding throughout the study and for 150 days after last dose.
			9 Subject has a negative TB Screening Assessment (including a PPD test and/or Quantiferon TB Gold test, or equivalent) and negative chest x-ray (CXR) (posterior anterior [PA] and lateral view). If the subject has evidence of a latent TB infection, the subject must initiate and complete a minimum of 2 weeks of an ongoing TB prophylaxis or have documented completion of a full course of TB prophylaxis prior to Baseline.
			10 Subject is judged to be in good general health, as determined by the Principal Investigator based upon the results of a medical history, physical examination, laboratory profile, chest x-ray, and a 12 lead electrocardiogram (ECG) performed during the Screening.

Exclusion Criteria

Yes	No	Not Applicable	
			1 Subject has erythrodermic psoriasis, guttate psoriasis, or subcorneal pustular dermatosis at Screening.
			2 Subject diagnosed drug-induced GPP.
			3 Total score of 14 or more in JDA severity index of GPP in GPP Medical Care Guideline 2014 in Japan.
			4 Subject has other active skin disease (e.g., urticarial, atopic dermatitis) or skin infections (bacterial, fungal, or viral) that may interfere with evaluation of GPP, with the exception of footpad trichophytosis (athlete's foot).
			5 Subject who cannot taper off cyclosporine until Week 8 after the Baseline and during the study. Subject who cannot taper etretinate to 20 mg/day at the maximum dose prior to the Baseline.

Yes	No	Not Applicable	
			6 Subjects who is receiving oral corticosteroid more than 10 mg/day at the Baseline, and cannot taper off until Week 4 after the Baseline and during study.
			7 Subject who received GMA (granulocyte and monocyte adsorption apheresis) therapy for at least 28 days prior to the Baseline and cannot avoid this therapy during the study.
			8 Subjects who received any investigational agents of chemical or biologic nature (including anti-IL17 agents), which would be efficacious to GPP or psoriasis-related skin disease for at least 28 days or 5 half-lives of the drug prior to the Baseline, whichever is longer, and during the study.
			9 Subjects who received ustekinumab for at least 84 days prior to the Baseline and during the study.
			10 Subject who cannot avoid PUVA or narrow-band UVB phototherapy for at least 14 days prior to the Baseline and during the study.
			11 Subject who cannot avoid "strongest" corticosteroid in Japanese classification of topical therapy for at least 14 days prior to the Baseline and during the study.
			12 Subject who cannot avoid anti-tumor necrosis factor (TNF) agent other than infliximab and adalimumab (including but not limited to etanercept [Enbrel], golimumab [Simponi] or certolizumab pegol [Cimzia]) for at least 28 days prior to the Baseline and during the study.
			13 Prior exposure to adalimumab.
			14 Subject who has previous used infliximab: 
 • and has not clinically responded at any time ("primary non-responder") unless subject experienced a treatment limiting reaction, or 
 • who used infliximab ("secondary treatment failure") within 42 days prior to the Baseline.
			15 Prior exposure to medications that have a potential or known association with progressive multifocal leukoencephalitis (PML) (i.e., natalizumab [Tysabri], rituximab [Rituxan], efalizumab [Raptive]).
			16 Subject with any active viral infection that makes the subject an unsuitable candidate for the study based on the investigator's clinical assessment.

Yes	No	Not Applicable	
			17 Hepatitis B: HBs Ag positive (+) or detected sensitivity on the HBV-DNA PCR qualitative test for HBC Ab/HBs Ab positive subjects.
			18 Subject with known hypersensitivity to the excipients of adalimumab.
			19 The subject is male, or female without childbearing potential
			20 The subject is male
			21 Female who is breast-feeding or considering becoming pregnant during the study.
			22 History of clinically significant drug or alcohol abuse in the last 12 months.
			23 History of demyelinating disease (including myelitis) or neurologic symptoms suggestive of demyelinating disease.
			24 History of moderate to severe congestive heart failure (NYHA class III or IV), recent cerebrovascular accident and/or any other condition which, in the opinion of the investigator, would put the subject at risk by participation in the study.
			25 Current evidence of dysplasia or history of malignancy (including lymphoma and leukemia) other than a successfully treated non-metastatic cutaneous squamous cell carcinoma, basal cell carcinoma or localized carcinoma in situ of the cervix.
			26 Chronic recurring infections or active TB.
			27 Infection(s) requiring treatment with intravenous (IV) anti-infectives (antibiotics, antivirals, antifungals) within 28 days prior to Baseline or oral anti-infectives (antibiotics, antivirals, antifungals) within 14 days prior to Baseline
			28 History of invasive infection (listeriosis, histoplasmosis), human immunodeficiency virus (HIV).

Yes No Not Applicable

 	28 Screening laboratory and other analysis show any of the following abnormal results: 
• AST, ALT $> 1.75 \times$ upper limit of the reference range;• WBC count $< 3.0 \times 10^9/L$;• Electrocardiogram (ECG) – with clinically significant abnormalities;• Total bilirubin ≥ 3 mg/dL; except for subjects with isolated elevation of indirect bilirubin relating to Gilbert syndrome.• Serum creatinine > 1.6 mg/dL.
 	29 Subject is considered by the Investigator, for any reason, to be an unsuitable candidate for the study.

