15. Prior exposure to medications that have a potential or known association with progressive multifocal leukoencephalopathy (PML) (i.e., natalizumab [Tysabri®], rituximab [Rituxan®], efalizumab [Raptiva®]).
16. Subject with any active viral infection that makes the subject an unsuitable candidate for the study based on the investigator's clinical assessment.
17. Hepatitis B: HBs Ag positive (+) or detected sensitivity on the HBV-DNA PCR qualitative test for HBc Ab/HBs Ab positive subjects.
18. Subject with known hypersensitivity to the excipients of adalimumab.
19. Positive pregnancy test at the Screening (serum) or the Baseline (urine).
20. Female who is breast-feeding or considering becoming pregnant during the study.
21. History of clinically significant drug or alcohol abuse in the last 12 months.
22. History of demyelinating disease (including myelitis) or neurologic symptoms suggestive of demyelinating disease.
23. History of moderate to severe congestive heart failure (NYHA class III or IV), recent cerebrovascular accident and/or any other condition which, in the opinion of the investigator, would put the subject at risk by participation in the study.

24. Current evidence of dysplasia or history of malignancy (including lymphoma and leukemia) other than a successfully treated non-metastatic cutaneous squamous cell carcinoma, basal cell carcinoma or localized carcinoma in situ of the cervix.
25. Chronic recurring infections or active TB.
26. Infection(s) requiring treatment with intravenous (IV) anti-infectives (antibiotics, antivirals, antifungals) within 30 days prior to Baseline or oral anti-infectives (antibiotics, antivirals, antifungals) within 14 days prior to Baseline.
27. History of invasive infection (e.g., listeriosis, histoplasmosis), human immunodeficiency virus (HIV).
28. Screening laboratory and other analysis show any of the following abnormal results:
 - AST, ALT $> 1.75 \times$ upper limit of the reference range;
 - WBC count $< 3.0 \times 10^9/L$;
 - Electrocardiogram (ECG) – with clinically significant abnormalities;
 - Total bilirubin ≥ 3 mg/dL; except for subjects with isolated elevation of indirect bilirubin relating to Gilbert syndrome;
 - Serum creatinine > 1.6 mg/dL.
29. Subject is considered by the Investigator, for any reason, to be an unsuitable candidate for the study.

Rationale for the Exclusion Criteria

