1, 2	To avoid medical conditions that may compromise the ability to identify subjects with the correct diagnosis or to interpret medical importance of clinical results
3, 18, 21	To exclude subjects who maybe at increased risk for protocol non-adherence or premature discontinue
4 – 15	To avoid bias for the evaluation of efficacy and safety by concomitant or prior use of other medications or treatments

16, 17, 19, 20, To reduce the risk to subjects or others and/or to exclude underlying
22 – 28 conditions that would compromise the subject's safety

29 To maintain the integrity of other aspects of study conduct, including,
subject sampling, treatment procedures, etc.

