5.2.3 Prior and Concomitant Therapy

5.2.3.1 Prior Therapy

Any non-GPP medication or vaccine (including over-the-counter or prescription medicines, vitamins, mineral supplements, and herbal supplements) that the subject is receiving within 30 days prior to Baseline, is receiving at the time of Enrollment, and/or receives during the study, must be recorded along with the reason for use, date(s) of administration including start and end dates, and dosage information including dose, route and frequency on the appropriate electronic case report form (eCRF). Medication for PPD test and injection solvents does not need to record as far as adverse events derived from these drugs are not occurred.

GPP-specific medications and therapies (including but not limited to cyclosporine, etretinate, MTX, oral or topical corticosteroids, topical vitamin D3, phototherapy, or GMA) that the subject has received within 90 days of Baseline should be recorded on the appropriate page of the eCRF and should include the date(s) of administration and dosages, and reason(s) for termination of the treatment (if appropriate). Subjects who failed to respond (within the past 1 year) or were intolerant (within the past 5 years) to treatment will have date(s) of administration, dosages including maximum dose, and reasons for discontinuation recorded in appropriate eCRF, as long as these information is available in the medical records.

For subjects previously treated with infliximab, the infliximab history will be recorded, including the duration of therapy, maximum dose, reason for use and reason(s) for termination of treatment.

The AbbVie SDP identified in Section [6.1.5](#) should be contacted if there are any questions regarding concomitant or prior therapies.

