5.3 Efficacy, Pharmacokinetic, and Safety Assessments/Variables

5.3.1 Efficacy and Safety Measurements Assessed and Flow Chart

Study procedures will be performed as summarized in Section 5.3.1.1. All subjects must meet the study selection criteria outlined in Section 5.2.1 and Section 5.2.2 in order to be enrolled into the study.

Table 1. Study Activities

Activity	Screening (Day -30 to Day -1)	Baseline ^a (Day 1)	Wk 2	Wk 4	Wk 8	Wk 12	Wk 16	Wk 20	Wk 24	Wk 28	Wk 32	Wk 36	Wk 40	Wk 44	Wk 48	Wk 52 or Premature Discontinuation Visit	Unscheduled Study Visit	70- Day Call
Informed Consent	X																	
Assign Subject ID Number	X																	
Subject Background	X																	
Inclusion/Exclusion Criteria	X	X ^b																
Medical/Surgical History	X	X ^b																
Prior and Concomitant Therapy Assessment	X	X ^b	X	X	X	X	X	X	X	X	X	X	X	X	X	X	X	
Alcohol Use	X																	
Tobacco Use	X																	
Physical Exam ^c	X	X	X	X	X	X	X	X	X	X	X	X	X	X	X	X	X	
Chest X-Ray/12-Lead ECG ^e	X															X ^f	X ^g	
TB Screening ^h	X																	
Vital Signs	X ⁱ	X	X	X	X	X	X	X	X	X	X	X	X	X	X	X	X	
Pregnancy Tests	X ^j	X ^k														X ^k		
General Labs ^l : Blood Chemistry and Hematology	X	X ^m	X	X	X	X	X	X	X	X	X	X	X	X	X	X ^s	X	

Table 1. Study Activities (Continued)

Activity	Screening (Day -30 to Day -1)	Baseline ^a (Day 1)	Wk 2	Wk 4	Wk 8	Wk 12	Wk 16	Wk 20	Wk 24	Wk 28	Wk 32	Wk 36	Wk 40	Wk 44	Wk 48	Wk 52 or Premature Discontinuation	Unscheduled Study Visit	70- Day Call
Urinalysis ⁿ	X	X														X		
HIV Screen ^o	X																	
Hepatitis B Screen ^p	X																	
Hepatitis C Screen	X																	
Antinuclear Antibody (ANA)/Anti-Double- Stranded DNA (dsDNA) ^q																		
Photography ^r	X	X	X	X	X	X	X	X	X	X	X	X	X	X	X	X		
GPP Skin Score and BSA, Systemic/Laboratory Score	X	X	X	X	X	X	X	X	X	X	X	X	X	X	X	X ^s		
PGA	X	X	X	X	X	X	X	X	X	X	X	X	X	X	X	X	X ^s	
PASI Score	X	X	X	X	X	X	X	X	X	X	X	X	X	X	X	X	X ^s	
DLQI		X														X		
SF-36		X														X		
Dispense Study Drug	X	X	X	X	X	X	X	X	X	X	X	X	X	X	X	X	X ^s	
Administer Study Drug ^t	X	X	X	X	X	X	X	X	X	X	X	X	X	X	X	X	X ^s	
PK Measurements ^u	X	X	X	X	X	X	X	X	X	X	X	X	X	X	X	X	X ^s	
AAA Measurements ^u	X	X	X	X	X	X	X	X	X	X	X	X	X	X	X	X	X ^s	

Table 1. Study Activities (Continued)

Activity	Screening (Day -30 to Day -1)	Baseline ^a (Day 1)	Wk 2	Wk 4	Wk 8	Wk 12	Wk 16	Wk 20	Wk 24	Wk 28	Wk 32	Wk 36	Wk 40	Wk 44	Wk 48	Wk 52 or Premature Discontinuation Visit	Unscheduled Study Visit	70- Day Call

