Monitor Adverse Events ^v	X	X	X	X	X	X	X	X	X	X	X	X	X	X	X	X	X	
Follow-Up Phone Call																	X ^w	

Footnote for Table 1:

- a. The Baseline visit date will serve as the reference for all subsequent visits. A \pm 7-days window is permitted around scheduled study visits.
- b. Update inclusion/exclusion, medical/surgical history, and prior and concomitant therapy information to assure subject eligibility.
- c. Physical examinations performed at Screening, Week 24 and Week 52/PD Visits will be full physical examinations. Physical exams performed at all other visits will be symptom-based.
- d. Chest x-ray (CXR) includes posterior-anterior [PA] **and** lateral views. Subjects with normal chest x-ray within 90 days of Screening will not require a repeat chest x-ray, if documentation is available.
- e. Subjects with normal ECG within 90 days of Screening will not require a repeat ECG, if documentation is available.
- f. Subjects will have a repeat CXR or ECG at Week 52 or the appropriate Premature Discontinuation visit, only if in the opinion of the investigator, clinically significant AEs develop during the study that warrant a repeat.
- g. Subjects can have a repeat CXR/ECG at any time during the study as warranted based on the opinion of the Investigator.
- h. Subjects with negative latent TB test(s) (In case a subject received both a PPD test and IGRA, both must be negative) within 90 days of Screening will not require a repeat latent TB test, if documentation is available. PPD skin test is to be read 48 to 72 hours after placement.
- i. Height will be measured at the Screening only.
- j. All females of childbearing potential will have a serum pregnancy test at the Screening that is performed at the central laboratory.
- k. All females of childbearing potential will have a urine pregnancy test at the Baseline and Week 52 or Premature Discontinuation visits at the central laboratory. Any subject with a positive urine pregnancy test must have a negative serum test performed at the central laboratory prior to start of the treatment in the study. Urine pregnancy test at the Baseline will be performed also at site to confirm negative result on site. If the result at site is positive, treatment with study drug should not be started until the serum pregnancy test at the central laboratory is confirmed negative.
- l. Subject should be fasting. Please refer to the laboratory manual for further instructions.

Table 1. Study Activities (Continued)

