7.0 Protocol Deviations

AbbVie does not allow intentional/prospective deviations from the protocol. The principal investigator is responsible for complying with all protocol requirements, and applicable global and local laws regarding protocol deviations.

For the purposes of the protocol, reportable deviations are defined as:

- Subject entered into the study even though she/he did not satisfy entry criteria
- Subject who developed withdrawal criteria during the study and was not withdrawn
- Subject who received wrong treatment or incorrect dose
- Subject who received excluded or prohibited concomitant treatment

If a protocol deviation occurs (or is identified) after a subject has been enrolled, the principal investigator is responsible for notifying IEC/Institutional Review Board (IRB), regulatory authorities (if appropriate), and the following AbbVie Clinical Monitor(s):

Primary Contact:

Alternate Contact:

Such contact must be made as soon as possible to permit a review by AbbVie to determine the impact of the deviation on the subject and/or the study.

The Investigator will record all protocol deviations in the appropriate medical records at site.

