3.0 Introduction

This statistical analysis plan (SAP) describes the statistical analysis to be completed by the AbbVie Global Statistics Department for adalimumab study Protocol M14-193 dated 06 April 2017, that incorporates administrative changes 1,2,3, and 4. (original protocol: 08 June 2015). It provides details to further elaborate statistical methods as outlined in the protocol and describes analysis conventions to guide the statistical programming work.

Unless noted otherwise, all analyses will be performed using SAS version 9.3 (SAS Institute Inc.) under the UNIX operating system or in the PC environment.

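### The Appendix E eligibility form gives a 28-day look-back for IV anti-infectives, but exclusion 26 in the synopsis and Section 5.2.2 gives 30 days

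*Protocol*

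**What the plan says.** Section 5.2.2, exclusion 26, reads "Infection(s) requiring treatment with intravenous (IV) anti-infectives (antibiotics, antivirals, antifungals) within 30 days prior to Baseline", followed by a 14-day window for oral anti-infectives. The synopsis has the same text and the same two numbers.

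The Appendix E form, which the site completes to document eligibility, reads "Infection(s) requiring treatment with intravenous (IV) anti-infectives (antibiotics, antivirals, antifungals) within 28 days prior to Baseline", again followed by 14 days for oral treatment. In the text supplied this line is numbered 27.

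Four other places bear on the point:

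- Section 5.3.1 says which text controls enrolment: "All subjects must meet the study selection criteria outlined in Section 5.2.1 and Section 5.2.2 in order to be enrolled into the study".
- The rationale at the end of Section 5.2.2 places exclusions 22 to 28 in the subject-safety group, beginning "To reduce the risk to subjects or others and/or to exclude underlying".
- Section 7.0 lists among reportable deviations: "Subject entered into the study even though she/he did not satisfy entry criteria".
- Section 5.3.1.1 has the site send its eligibility results to the sponsor's CRA within 5 days of the Baseline assessment and keep the eligibility worksheet as a source document.

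**The concern.** The form is where the site records each criterion as met or not met. If its threshold is looser than the protocol's, a site can complete it truthfully and still pass someone whom the protocol excludes. Here that is a subject whose IV treatment was last needed on day 29 or 30 before Baseline. A monitor reading only the form would see nothing wrong.

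The criterion is a safety one, applied before starting a TNF inhibitor. Section 6.3 treats infections that need IV anti-infectives seriously enough to interrupt dosing. Enrolling such a subject would be a reportable deviation, and in this case the protocol's own form would have prompted it.

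**Working it through.** No power or sample-size figure is involved. The check compares the three statements of the criterion.

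| Place | IV look-back | Oral look-back |
|---|---|---|
| Synopsis, exclusion 26 | 30 days | 14 days |
| Section 5.2.2, exclusion 26 | 30 days | 14 days |
| Appendix E form | 28 days | 14 days |

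**Same criterion?** Yes. The wording matches apart from the IV number, and the oral window is identical. The item number on the form is offset from Section 5.2.2, and 28 is printed there twice, but the content leaves no doubt which exclusion is meant.

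**Size of the gap.** IV: 30 − 28 = 2 days, namely days 29 and 30 before Baseline. Oral: 14 − 14 = 0.

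**Direction.** The form is the looser text. It can pass a subject whom Section 5.2.2 excludes, but on this criterion it cannot exclude one whom Section 5.2.2 admits.

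**Which number is intended?** Thirty days. It stands in the controlling section and in the synopsis. Section 5.2.3.1 also requires non-GPP medication to be recorded if it is something "that the subject is receiving within 30 days prior to Baseline, is receiving at the time of Enrollment". That is a general recording rule, not one derived from exclusion 26, so it is consistent with 30 days but adds little weight.

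**Superseded or missing text?** Neither. All three statements are in the body of the supplied protocol, none comes from a change log, and nothing is redacted at this point.

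**The case against.** The strongest reply is that the form does not define eligibility. Sections 5.1, 5.2, 5.3.1 and 5.5.3 all tie enrolment to Sections 5.2.1 and 5.2.2, and the investigator makes the final assessment against those criteria. The form only records and transmits that decision. Other checks exist too. An IV anti-infective on day 29 or 30 falls inside the 30-day medication record. Table 1, footnote b, requires the site at Baseline to "Update inclusion/exclusion, medical/surgical history, and prior and concomitant therapy information to assure subject eligibility". Section 11.0 provides for source verification, and exclusions 23 and 29 leave the investigator discretion. These points stand, and they keep this a minor matter. They do not make the form correct. The checks that fall to the sponsor may also come late, because eligibility results may be sent up to 5 days after the assessment and eCRF entry is due within 5 days of a visit, so either can follow the first dose.

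A second reply concerns the text itself. The form's numbering is irregular around this line, possibly from reading the PDF, so the printed item number 27 may not be reliable. That is a good reason to locate the line by its wording. Nothing suggests that the 28-day figure itself was misread.

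A third concerns the version. The supplied synopsis is dated 08 June 2015, whereas Section 3.0 of the SAP cites a protocol dated 06 April 2017 "that incorporates administrative changes 1,2,3, and 4". The form may already have been corrected, and these documents cannot settle that.

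**Conclusion.** The inconsistency is real: the form's IV look-back is 2 days shorter than the protocol's, and the form is the outlier. It is a small correction. As a share of the window the gap is 2/30 = 6.7%, but that is not a probability that any subject is affected. The documents do not say how often candidates receive IV anti-infectives, so no count of affected subjects is offered. The 10-subject sample size, the power statement and the Week 16 analysis do not change.

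The conclusion assumes that the supplied text reproduces the form's number correctly. Whether a correction is still needed depends on the 2017 protocol version, which was not available.

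**What to change.** First check the form in the protocol version dated 06 April 2017. If the IV anti-infective line still says 28 days, change it to 30 and leave the oral window at 14. Identify the line by its content, not by its item number. The synopsis and Section 5.2.2 need no edit.

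The cost is one number on one form, with no added visits, procedures or subjects. The sponsor can decide the administrative route.
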